5.5 Derived Variables

All questionnaire scores will be derived by Biostatistics in the ADaM datasets using the formulas defined below, even if calculated scores are present in the EDC database. All pre-calculated scores will be ignored for analysis.

- With the following exception, vIGA-AD Score of Clear (0) or Almost Clear (1) = vIGA-AD of ‘Clear’ (0) or ‘Almost Clear’ (1). The exception is that for subjects who discontinued early from study due to an AE or lack of efficacy, the subject will be considered as not having a vIGA-AD score of Clear (0) or Almost Clear (1) for all pre-specified analysis visits (refer to Section 5.4) for which the subject’s day of last dose falls within or is before the start of the analysis visit window.
- With the following exception, vIGA-AD Success = vIGA-AD of ‘Clear’ (0) or ‘Almost Clear’ (1) plus at least a 2-grade improvement from baseline. The exception is that for subjects who discontinued early from study due to an AE or lack of efficacy, the subject will be considered as not having a vIGA-AD success for all pre-specified analysis visits (refer to Section 5.4) for which the subject’s day of last dose falls within or is before the start of the analysis visit window. vIGA-AD Success will be derived for both the Primary and OLE baselines (refer to Section 5.2)
- Date of last contact = the latest of last study visit date, last dose date, end-of-study date and end-of-treatment date.
- Post-OLE Week 4 study duration (days): The duration can be represented as End Date – Start Date +1. The start date of the Post-OLE Week 4 interval will be the date of the OLE Week 4 visit or OLE Day 29 if the subject missed the OLE Week 4 visit. The end date will be the date of last contact. This endpoint will be calculated only for subjects who enter the post-OLE Week 4 study period.
- Duration (days) of the first BIW dosing will be calculated from the first BIW dosing to the start of the succeeding QD dosing interval. Subject’s last contact date will be used to censor

 Innovaderm Research	STATISTICAL ANALYSIS PLAN, Final Version 1.0
Protocol Number: ARQ-151-313	Sponsor: Arcutis Biotherapeutics, Inc.

this endpoint (time-to-event analysis) or as the end date of this duration (analyzed as a continuous endpoint) for subjects who do not revert to a QD dosing regimen after the first BIW dosing. This endpoint will be calculated only for subjects who enter the post-OLE Week 4 study period with at least one BIW dosing interval.

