- Cumulative time (days) on BIW dosing: Subjects may have more than 1 BIW dosing interval. The duration of succeeding BIW dosing intervals will be derived in a manner similar to the first and durations will be summed across all intervals for a subject. This endpoint will be calculated only for subjects who enter the post-OLE Week 4 study period with at least one BIW dosing interval.
- Percent of time on BIW dosing: The cumulative time (days) on BIW dosing will be divided by the Post-OLE Week 4 study duration and multiplied by 100 to measure the percentage of study days on BIW dosing. This endpoint will be calculated only for subjects who enter the post-OLE Week 4 study period with at least one BIW dosing interval.
- Duration (days) of first disease control will be calculated from the first disease control to the time subjects revert to a QD dosing or have a vIGA-AD score ≥ 2 , whichever comes first. Disease control is defined as achievement of a vIGA-AD score of 0, a switch to BIW dosing, and maintenance of a vIGA-AD score of 0 or 1. Disease control starts with the later date of a vIGA-AD score of Clear (0) on or after OLE Week 4 and the switch to BIW dosing. Subject's last contact date will be used to censor this endpoint (time-to-event analysis) or as the end date of this duration (analyzed as a continuous endpoint) for subjects who never lose disease control after the start of the first disease control interval. This endpoint will be calculated only for subjects who enter the post-OLE Week 4 study period and had at least one disease control interval.
- Cumulative time (days) with disease control. Subjects can come in and out of disease control. The duration for each interval will be derived as described above for the first interval. Cumulative time with disease control will sum the durations for all intervals where disease was under control as defined in the previous bullet. This endpoint will be calculated only for subjects who enter the post-OLE Week 4 study period and had at least one disease control interval.
- Percent of time with disease control. The cumulative time with disease control will be divided by the Post-OLE Week 4 study duration and multiplied by 100 to express cumulative time as a percentage of the duration of time that each subject spent in the study after OLE Week 4. This endpoint will be calculated only for subjects who enter the post-OLE Week 4 study period and had at least one disease control interval.

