 Innovaderm Research ■■■	STATISTICAL ANALYSIS PLAN, Final Version 1.0
Protocol Number: ARQ-151-313	Sponsor: Arcutis Biotherapeutics, Inc.

- Duration (days) of the first vIGA-AD of Clear (0) will be calculated from the first vIGA-AD score of 0 during the study to the next vIGA-AD score > 0. Subject's last contact date will be used to censor this endpoint (time-to-event analysis) or as the end date of this duration (analyzed as a continuous endpoint) for subjects who never revert to a vIGA-AD score > 0. This endpoint will be calculated only for subjects who had at least one vIGA-AD score of Clear (0) interval.
- Cumulative time (days) with vIGA-AD of Clear (0). Subjects can have more than 1 vIGA-AD of Clear (0) interval. The duration for each interval will be derived as described above for the first interval. Cumulative time with vIGA-AD of 0 will sum the durations for all intervals. This endpoint will be calculated only for subjects who had at least one vIGA-AD score of Clear (0) interval.
- Percent of time with vIGA-AD of Clear (0). The cumulative time will be divided by the study duration and multiplied by 100 to express cumulative time as a percentage of the duration of time that each subject spent in the study. This endpoint will be calculated only for subjects who had at least one vIGA-AD score of Clear (0) interval.
- Duration (days) of the first vIGA-AD of Clear (0) or Almost Clear (1) will be calculated from the first vIGA-AD score of 0 or 1 during the study to the next vIGA-AD score > 1. Subject's last contact date will be used to censor this endpoint (time-to-event analysis) or as the end date of this duration (analyzed as a continuous endpoint) for subjects who never revert to a vIGA-AD score > 1. This endpoint will be calculated only for subjects who had at least one VIGA-AD with a score of Clear (0) or Almost Clear (1) interval.
- Cumulative time (days) with vIGA-AD of Clear (0) or Almost Clear (1). Duration with vIGA-AD score of 0 or 1 measures the duration for the first interval with a VIGA-AD score of 0 or 1. There can be more than 1 interval. Cumulative time with vIGA-AD of 0 or 1 will sum the durations for all intervals. The duration for each interval will be derived as described above for the first interval. This endpoint will be calculated only for subjects who had at least one VIGA-AD with a score of Clear (0) or Almost Clear (1) interval.

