12.3.1 Main Analysis

Missing other efficacy endpoints will not be imputed.

Duration, cumulative time, and percent of time endpoints will be summarized using descriptive statistics by treatment group (refer to Section 5) and two-sided 95% CI of the mean will also be provided.

For duration endpoints, the number and percentage of subjects experiencing a status change or censored will be provided overall and by treatment group, along with reason for censoring. Additionally, these endpoints will also be analyzed using Kaplan–Meier (KM) method. The KM estimates of the time-to-event will be provided overall and by treatment group for the 25th, 50th (median), and 75th percentiles along with their corresponding two-sided 95% CI. The estimates of the SEs will be computed using the Greenwood's formula. The two-sided 95% CI for the survival function at the 25th, 50th, and 75th percentiles will be calculated according to Brookmeyer and Crowley (1982)². KM curves will be provided overall and by treatment group.

Dichotomic, change from baseline, and percent change from baseline endpoints will be summarized similarly as the secondary efficacy endpoints (refer to Section 12.2).

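### First-interval durations still open at last contact are averaged as if complete; for BIW dosing the reported mean and 95% CI describe follow-up-limited time, not duration

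*SAP*

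**What the plan says.** SAP 5.5 (Derived Variables) defines four first-interval durations: BIW dosing, disease control, vIGA-AD clear, and vIGA-AD clear or almost clear. Each has two versions. For BIW dosing, last contact acts as the censoring date for "this endpoint (time-to-event analysis) or as the end date of this duration (analyzed as a continuous endpoint) for subjects who do not revert"; reverting here means returning to QD dosing. For disease control it serves "as the end date of this duration (analyzed as a continuous endpoint) for subjects who never lose disease control". The two vIGA-AD durations follow the same pattern; the one for clear skin reads "analyzed as a continuous endpoint) for subjects who never revert to a vIGA-AD score > 0". Last contact is defined broadly: "Date of last contact = the latest of last study visit date, last dose date, end-of-study date and end-of-treatment date".

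SAP 12.3.1 says that the duration, cumulative-time and percent-of-time endpoints are "summarized using descriptive statistics by treatment group (refer to Section 5) and two-sided 95% CI of the mean will also be provided". By SAP 5.6, descriptive statistics include the median, Q1 and Q3. The treatment groups in SAP 5 pool Cohort-Week 24 with Cohort-Week 52.

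SAP 12.3.1 adds, for durations, that "the number and percentage of subjects experiencing a status change or censored will be provided overall and by treatment group", with reasons for censoring, and that "these endpoints will also be analyzed using Kaplan–Meier (KM) method", giving quartiles with 95% CIs and curves. SAP 6.6 repeats these endpoints by cohort for ARQ-151-311/312 rollovers.

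**The concern.** An interval that has not ended has no observed duration. The time-to-event version recognises this; the continuous version enters the time to last contact as if the interval had finished. The mean then estimates E[min(T, follow-up)], where T is the interval length, and follow-up differs by design: 24 or 52 weeks. The attached 95% CI invites the reader to take the figure as an estimate of mean duration.

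Two things are at stake. SAP 6.6 uses the BIW and disease-control endpoints to examine long-term maintenance of effect, so a mean with a CI will be read as a durability result. And the naive quartiles will be printed for the same endpoint as the Kaplan-Meier quartiles, with no statement of which governs.

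**Working it through.** The plan gives no numerical duration, so there is no figure to reproduce. The check asks what the planned mean estimates.

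**Inputs**
- Target days 29, 169 and 365 (SAP 5.4, Table 3). An interval starting at Week 4 has at most 169 − 29 = 140 days in Cohort-Week 24 and 365 − 29 = 336 days in Cohort-Week 52.
- Distribution of true durations: not in the documents. Assumed exponential with median M, so mean m = M / ln 2.
- Cohort-Week 24 share among subjects with an interval: not given. The Protocol's Summary of Changes gives about 275 + 275 = 550 such subjects, and 550 / 1500 = 37% of planned enrolment. Range tried: 25% to 50%. Cohort-Week 24 comes only from ARQ-151-311/312, and rollovers from ARQ-151-315 are tabulated separately, so the share in the 311/312 table could be higher, which would lower the pooled mean further.

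**Formulas** (interval starting at Week 4, maximum follow-up τ)
- Naive mean = m(1 − exp(−τ/m))
- Proportion censored = exp(−τ/m)

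**Worked case, M = 200.** m = 200 / 0.693 = 289 days.
- Cohort-Week 24: exp(−140/289) = 0.62 censored; naive mean 111.
- Cohort-Week 52: exp(−336/289) = 0.31 censored; naive mean 198.
- Pooled: 0.25 × 111 + 0.75 × 198 ≈ 177; at 37%, 166; at 50%, 155.

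**Other medians, first BIW interval**

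| True median | True mean | Naive, Wk 24 (censored) | Naive, Wk 52 (censored) | Pooled at 37% |
|---|---|---|---|---|
| 60 | 87 | 69 (20%) | 85 (2%) | 79 |
| 120 | 173 | 96 (45%) | 148 (14%) | 129 |
| 240 | 346 | 115 (67%) | 215 (38%) | 178 |
| 360 | 519 | 123 (76%) | 247 (52%) | 201 |

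**CI coverage.** Simulation with 1000 runs of 200 subjects, 37% Cohort-Week 24, assumed staggered starts at visit days and no early dropout. The nominal 95% CI covered the true mean in 28% of runs at a true median of 60 days, and in none at 120, 240 or 360.

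**Conflict with Kaplan-Meier.** At M = 200, a fraction 1 − 0.616 = 0.384 of intervals end before day 140, and open Cohort-Week 24 intervals pile up at day 140. At a 25% share, 0.384 + 0.25 × 0.616 = 0.538, already above one half. The naive median is therefore 140 days, while Kaplan-Meier targets 200.

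**Interim.** SAP 6.3 runs all planned analyses at the interim analysis. More intervals are open then, so the naive mean can rise by the final analysis with no change in durability.

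**vIGA-AD durations.** These end at the next score above threshold. Scheduled assessments after Week 4 are 56, 84, 84 and 112 days apart, so loss is dated late, and last contact may fall after the last assessment. Simulating clear skin from Week 4, with loss seen only at visits:

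| True median | 30 | 60 | 120 | 240 | 480 |
|---|---|---|---|---|---|
| Bias, Cohort-Week 24 | +83% | +16% | −33% | −63% | −81% |
| Bias, Cohort-Week 52 | +92% | +44% | +7% | −30% | −59% |

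Disease control ends at return to QD or at vIGA-AD of 2 or more, whichever is first, so it mixes both mechanisms.

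**The case against.** The strongest reply is that the valid analysis is already in the plan. Kaplan-Meier quartiles and curves, censoring counts with reasons, and the cohort split in SAP 6.6 are all pre-specified. These are other efficacy endpoints in a safety study, SAP 5.7 plans no hypothesis test, and no decision rule uses the mean. All of that stands and limits the consequence. It does not make the extra summary valid: the cohort split removes the dependence on mix but not the truncation, and the naive mean, CI and quartiles would still be printed for the same endpoint as the Kaplan-Meier results.

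Three stronger readings might be inferred, and the documents do not support them:
- *All four durations are biased low.* The two vIGA-AD durations end only at an assessment, which lengthens short intervals, so the sign depends on the true duration.
- *The mean tracks cohort mix and not drug effect.* At a fixed 37% mix it rises 79, 129, 178, 201 as the true median goes 60, 120, 240, 360. It responds, but weakly: 201 / 79 = 2.5-fold against 519 / 87 = 6-fold in the true mean.
- *No valid analysis of duration is planned.* SAP 12.3.1 plans one.

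**Conclusion.** The concern holds as a defect in one of two planned summaries. For the first BIW interval, the continuous mean is a follow-up-limited quantity. Read as mean duration, it is low by 20% to 76% in Cohort-Week 24 and 2% to 52% in Cohort-Week 52 for true medians of 60 to 360 days, and its CI fails once censoring is common. Disease control shares this in part. For the two vIGA-AD durations the bias can go either way.

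That open intervals are closed at last contact and averaged with a CI follows directly from the SAP. The sizes rest on assumptions: exponential durations, closed-form figures for Week 4 starts only, and an unknown cohort share. The change is worth making, but no test or primary conclusion depends on it.

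**What to change.** In SAP 12.3.1, name Kaplan-Meier as the summary for the four duration endpoints, and remove the naive mean, its 95% CI and the naive quartiles. Alternatively, keep descriptive figures without a CI, by cohort only, labelled *observed time to event or last contact*.

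If a mean is wanted, report a Kaplan-Meier restricted mean by cohort to a common horizon that enough subjects in both cohorts can reach, given their interval start dates. A 140-day horizon is reachable in Cohort-Week 24 only for intervals starting at Week 4; one starting at Week 12 (day 85) has 169 − 85 = 84 days.

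The cost is SAP wording and one table removed, relabelled or replaced; no new data are needed. The downside is that under heavy censoring the Kaplan-Meier median may not be estimable: in the simulation it was reached in only 30% of runs at a true median of 360 days. The change also leaves the dating of vIGA-AD loss at visits as it is, under Kaplan-Meier as well.

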4. INVESTIGATIONAL PLAN

4.1. Overall Study Design and Plan

This is a Phase 3, open-label, single-arm, long-term safety study in which ARQ-151 cream 0.15% or ARQ-151 cream 0.05% is applied QD x 24 (Cohort-Week 24) or 52 weeks to subjects with mild to moderate atopic dermatitis (except for time on BIW maintenance therapy).

- Eligible subjects will enroll into the long-term safety study on the same day as the Week 4 visit of the preceding study (ARQ-151-311 or ARQ-151-312 or ARQ-151-315).
- Subjects/caregivers will apply ARQ-151 cream 0.15% for subjects \geq 6 years old or ARQ-151 cream 0.05% for subjects 2-5 years old.
- If a 5 year-old subject turns 6 years-old during this study, the subject will be switched from ARQ-151 cream 0.05% to ARQ-151 cream 0.15% at his/her first scheduled post-birthday visit. Dose reduction back to 0.05% is not permitted.
- The study drug will be applied QD for 24 (Cohort-Week 24) or 52 weeks to all AD affected areas and any newly appearing AD lesions that arise during the study, except on the scalp (unless entering BIW maintenance therapy, as described below).
- **For the first 4 weeks of study ARQ-151-313, all subjects will apply study medication QD in the areas identified and treated as per the body diagram in the preceding study (ARQ-151-311/312/315).** Beginning at the Week 4 visit, any subject who achieves vIGA-AD of '0-clear' as confirmed by the Investigator at a scheduled or unscheduled clinic visit, will switch to twice weekly (BIW) maintenance treatment. For maintenance therapy, study medication will be applied on two nonconsecutive days per week (e.g. Monday and Thursday) to areas commonly and/or most recently affected by AD, and any areas where AD is developing. Subjects receiving maintenance treatment who experience AD worsening (signs and symptoms) for 1 week despite dosing twice weekly will phone the clinical study site, resume daily dosing, and complete the subject diary accordingly. The phone call (but not a clinic visit) is required to resume daily dosing. At clinic visits, subjects receiving maintenance treatment may continue twice weekly maintenance dosing if vIGA-AD is either '0-clear' or '1-almost clear'. Subjects will resume daily dosing if vIGA-AD \geq 2, and can resume daily dosing if signs/symptoms of AD are not adequately controlled with maintenance therapy despite vIGA-AD of '1-almost clear'.

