5.2.1. Validated Investigator Global Assessment scale for Atopic Dermatitis

Validated Investigator Global Assessment scale for Atopic Dermatitis (vIGA-AD) assessments should be completed prior to other physician assessments.

vIGA-AD assessment will be performed according to the Schedule of Visits and Assessments ([Section 1.3](#)). The vIGA-AD is a static evaluation of qualitative overall AD severity. This global assessment scale is an ordinal scale with five severity grades (reported only in integers of 0 to 4). Each grade is defined by a distinct and clinically relevant morphologic description that minimizes inter-observer variability (see [Appendix 5](#)). vIGA-AD is evaluated for the entire body except the scalp, palms, and soles.

Note: All atopic dermatitis lesions on a subject will be treated including the face, trunk, genitals/skin folds, or limbs (excluding the scalp). The palms and soles will be treated but will not be counted towards any measurements of efficacy (EASI, vIGA-AD, BSA).

Every effort must be made for the same Evaluator to complete the IGA for the subject at every study visit.

IGA will be assessed at clinic visits.

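### First-interval vIGA-AD clear durations date loss at the visit that records it and run open intervals to last contact, so they come out too long

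*SAP*

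**What the plan says.** SAP 5.5 defines the first Clear (0) duration by recorded scores alone: it "will be calculated from the first vIGA-AD score of 0 during the study to the next vIGA-AD score > 0". The Clear or Almost Clear version has the same structure: it "will be calculated from the first vIGA-AD score of 0 or 1 during the study to the next vIGA-AD score > 1". If no such score follows, the date of last contact closes the interval in the descriptive summary and censors it in the time-to-event analysis. "Date of last contact = the latest of last study visit date, last dose date, end-of-study date and end-of-treatment date". Cumulative time is built from the same pieces: "Cumulative time with vIGA-AD of 0 will sum the durations for all intervals".

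Protocol 5.2.1 states that "IGA will be assessed at clinic visits". The schedule (Protocol 1.3) places them at Weeks 4, 12, 24, 36 and 52, or Weeks 4, 12 and 24 for Cohort-Week 24. The phone visits at Weeks 18, 30 and 44 carry no vIGA-AD. From Week 4, a subject scored 0 moves to twice-weekly dosing. If AD then worsens for a week, Protocol 4.1 says: "The phone call (but not a clinic visit) is required to resume daily dosing".

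The companion endpoint in SAP 5.5 does use that event: "Duration (days) of first disease control will be calculated from the first disease control to the time subjects revert to a QD dosing", or to a score of 2 or more if that comes first.

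In SAP 12.3.1, "For duration endpoints, the number and percentage of subjects experiencing a status change or censored will be provided overall and by treatment group", followed by Kaplan-Meier percentiles and curves. SAP 12.3.2 plans no sensitivity analysis for these endpoints.

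**The concern.** Three features of the rule lengthen the first interval.

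- **Late dating.** A loss between two visits is dated at the later visit, and Kaplan-Meier treats that date as exact.
- **Bridging.** A subject who flares, returns to daily dosing by phone and is scored 0 at the next visit has no recorded loss. Protocol 5.7.1 generally keeps ordinary AD worsening out of the adverse event data, so those data will not recover it.
- **Open intervals.** Last contact can fall after the last score. Protocol 4.7.6 declares loss to follow-up only after repeated phone and email attempts and a certified letter, so the end-of-study date may be well past the last assessment. That unassessed time counts as clear, and in Kaplan-Meier the subject stays at risk while no loss can be observed.

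At stake is the figure a reader would take as how long subjects stay clear once they are clear.

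**Working it through.** **Visit gaps.** SAP Table 3 target days follow 7 × week + 1. For Weeks 4, 12, 24, 36 and 52 this gives 29, 85, 169, 253 and 365, as printed. The gaps are 56, 84, 84 and 112 days. With the visit windows they range over 46–66, 70–98, 70–98 and 98–126 days. A single loss falling evenly within a gap is dated late by half of it on average: 4, 6, 6 or 8 weeks.

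**One subject (assumed dates).** Clear on day 29; flare on day 43; phone call and QD on day 50; re-cleared on day 71; scored 0 on day 85; lost again on day 100; scored above 0 on day 169.
- SAP first Clear duration: 169 − 29 = 140 days.
- Days truly clear: (43 − 29) + (100 − 71) = 14 + 29 = 43, of which the first spell is 14.
- Disease control ends at QD: 50 − 29 = 21 days.

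**Kaplan-Meier median, 52-week schedule.** The documents give no spell lengths, so everything below is assumed: scored 0 at Week 4, exponential spells, scheduled visits only, and a true median first spell of 60 days. Then λ = ln 2 / 60 = 0.01155 per day. Let μ = 1 / (mean days to re-clear). For a gap g,

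P(clear at next visit | clear now) = μ/(λ+μ) + [λ/(λ+μ)] × exp(−(λ+μ)g).

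With 28 days to re-clear, μ = 0.03571, λ+μ = 0.04727 and μ/(λ+μ) = 0.7556. For g = 56: 0.7556 + 0.2444 × 0.0709 = 0.773. For g = 84: 0.760. The observed proportion still clear is 0.773 at day 56, 0.773 × 0.760 = 0.588 at day 140, and 0.588 × 0.760 = 0.447 at day 224. The median is reported as 224. With no re-clearing the proportion is exp(−λt).

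| Mean days to re-clear | Day 56 | Day 140 | Day 224 | Day 336 | Reported median |
|---|---|---|---|---|---|
| none | 52% | 20% | 8% | 2% | 140 |
| 42 | 72% | 49.6% | 34% | 23% | 140 |
| 28 | 77% | 59% | 45% | 34% | 224 |
| 21 | 81% | 65% | 53% | 42% | 336 |
| 14 | 86% | 74% | 64% | 55% | not reached |

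Days are counted from Week 4. Cohort-Week 24 has no scheduled visit beyond day 140.

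**Simulation.** Mean clear spells of 42, 84 or 168 days and mean flares of 14, 28 or 56 days (assumed) were run on the 52-week schedule. Between 32% and 79% of first losses were not seen at the next visit. With 84 and 28 days, the true median was 58 days and the SAP rule gave 224.

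**Percent of time clear.** Re-clearance is also dated late, which offsets much of the error. With 84 and 28 days the result was 76.6% true against 79.5% by the SAP rule. The excess was about 1 to 7 points over the grid and 7 to 8 points in two Week 24 runs. If subjects are instead in steady state at Day 1, with a 60-day median and 28 days to re-clear, the chance of a score of 0 is 0.756 at every visit. The expected credited share then equals the true share (75.6% against 75.5% when simulated).

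**The case against.** The strongest reply is that the BIW and disease-control endpoints already stop at return to QD, and SAP 6.6 names those two when it sets out to examine long-term maintenance. A phoned-in flare is therefore captured where the plan looks for it. The Clear durations are other efficacy endpoints in a single-arm safety study with no hypothesis tests. This stands, and it limits the importance of the point.

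Several stronger readings are tempting but not supported:

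- *All three clear-time measures are materially inflated.* The large distortion is in the first interval. Cumulative and percent time move little, and not at all in the steady-state case.
- *The SAP contradicts itself by allowing control lost and skin clear on the same dates.* Disease control combines a score with a dosing rule, while Clear uses the score alone. These are different constructs.
- *Scores exist only at Weeks 4 to 52, so medians can take only a few values.* Scores also come from Day 1 (4 weeks before Week 4), unscheduled visits and early-termination visits, and visit windows spread the dates. An unscheduled visit is not required for a flare, however.
- *AD relapses faster than the visits are spaced.* The documents give no spell lengths.

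Last-contact censoring matters mainly for subjects with no final assessment. Completers are scored at their last visit, and a withdrawing subject is due a termination visit with the same procedures (Protocol 5.5).

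Finally, redefining Clear by a dosing change would replace an investigator score with a subject-reported trigger and make the endpoint largely overlap disease control. That is a fair reason not to make it the main definition.

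**Conclusion.** The point holds for the first-interval vIGA-AD 0 and 0/1 durations. Measured from the first recorded qualifying score, they are biased long, because loss is visit-dated, short flares can be bridged, and open intervals may include unassessed time. The direction follows from the documents. The size does not: 140, 224, 336 or not reached against a true median of 60 days depends on assumed exponential spells and assumed re-clearing times. Net bias in cumulative and percent time is modest, about 0 to 8 points in the cases run. Primary safety and secondary efficacy endpoints are untouched. This is a cheap improvement to descriptive analyses and does not threaten the study's conclusions.

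**What to change.** - **SAP 5.5:** close or censor open vIGA-AD 0 and 0/1 intervals at the last vIGA-AD assessment instead of last contact. Keep the score-based definition as the main one, labelled as time between clear assessments.
- **SAP 12.3.1:** estimate the first-interval vIGA-AD durations as interval-censored (Turnbull), with loss placed between the last qualifying and the first non-qualifying score. In the no-re-clearing example this puts the median between days 56 and 140, where Kaplan-Meier reports the upper end.
- **SAP 12.3.2:** Turnbull cannot recover a bridged flare, so add a sensitivity analysis that also ends the interval at the recorded return to QD for AD worsening. The dates come from the dosing diary (Protocol 4.7.4) and are already needed for the BIW endpoints. This marks only flares in subjects on BIW. A subject scored 1 who never left daily dosing leaves no such date.

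The cost is SAP wording and some extra programming; no visit, dose or assessment changes. Reported clear durations will become shorter and less precise.
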